4. INVESTIGATIONAL PLAN

4.1. Overall Study Design and Plan

This trial will be a randomized, placebo controlled, double-blind (within dosing group), dose escalation Phase 1 trial evaluating dosages of 1 mcg and 5 mcg of HydroVax-002 YFV vaccine given intramuscularly on Day 1 (the day of first vaccination is defined as Day 1) and Day 29 in healthy adults ≥ 18 and < 50 years of age. The study will consist of two dosing groups of HydroVax-002 YFV vaccine to be enrolled sequentially. Each dose group will consist of 10 individuals who receive HydroVax-002 YFV and 2 or 3 who receive placebo. The initial dose of HydroVax-002 YFV to be evaluated in Group 1 will be 1 mcg and the next dose to be evaluated in Group 2 will be 5 mcg. Following assessment of safety and reactogenicity data of Group 1 by the Safety Monitoring Committee (SMC), the vaccine dose will be increased to 5 mcg for Group 2. All participants will be monitored for local and systemic solicited adverse events for 7 days following each vaccination, unsolicited adverse events for 28 days following each vaccination, and for the occurrence of new onset chronic medical conditions and serious adverse events from the time of first vaccination until 6 months following the second vaccination. Safety laboratory tests will be performed prior to vaccination and at days 4 and 15 following vaccination. YFV neutralizing assays will be performed on blood samples collected prior to each vaccine, 15 days following each vaccine, and at days 29, 57, and 180 following the second dose of vaccine.

For each dosing group, the first four subjects enrolled (the sentinel subgroup) will include three HydroVax-002 YFV recipients and one placebo recipient. After the four subjects in the Group 1 sentinel subgroup are enrolled and given their first vaccination, enrollment will then be stopped pending a review of the clinical laboratory, reactogenicity, and safety data collected through the post vaccination Day 8 visit for the last of those subjects. This review may be conducted by an internal safety review committee (ISRC), consisting of the medical monitor, medical officer, clinical program manager, and the PI, or by the SMC, as indicated and detailed in complete clinical protocol. Approval by the reviewing group will allow administration of the second vaccination to the sentinel subgroup and continued enrollment of the remaining 9 Group 1 subjects (expanded group) to resume to complete enrollment of 13 participants (10 vaccine and 3 placebo).

After Group 1 enrollment is completed, enrollment will be stopped pending an SMC review of the clinical laboratory, reactogenicity, and adverse event information through the post 2nd vaccination Day 15 visit for all Group 1 subjects. Approval by the SMC will allow escalation to Group 2, and initiation of enrollment of the Group 2 sentinel subgroup. After the four subjects in the Group 2 sentinel subgroup are enrolled and given their first vaccination, enrollment will then be stopped pending a safety review of the sentinel subgroup as specified for the low dose cohort. Approval will allow administration of vaccination 2 to the sentinel subgroup and continued enrollment of Group 2 subjects (expanded group) to complete study enrollment.

This study will accrue 25 participants: (10 receiving 1 mcg of HydroVax-002 YFV; 10 receiving 5 mcg of HydroVax-002 YFV; and 5 receiving placebo).

The full schedule of events is provided in the complete clinical protocol.

4.2. Discussion of Study Design, Including the Choice of Control Groups

For this Phase 1 first-in-human trial, a conservative dose escalation design will be used, in which each dose group of 10 vaccine recipients, and a total of 5 placebo recipients is split into two subgroups. The first subgroup, termed the sentinel subgroup, includes 3 vaccine and 1 placebo recipient. In each of the two (1 mcg and 5 mcg) dose phases, enrollment is halted after vaccination of the sentinel subgroup. This allows the opportunity to identify early vaccine related adverse events in this subgroup prior to exposure of additional

subjects, a design which decreases the risk of multiple serious vaccine related adverse events compared to sequential vaccination of the entire dose group without halting. After enrollment of the expanded subgroups, escalation to the next dose group will be delayed until 14 days of safety data following the second vaccination (corresponding to study Day 15) is available from all subjects in the preceding dose group.

Placebo recipients are included in order to maintain blinding, provide some safety reference data, and to provide controls for the immunogenicity assays.

4.3. Selection of Study Population

[figure not shown]
This is the first human trial of HydroVax-002 YFV, thus the study population is healthy individuals ages ≥ 18 and < 50 years.

4.4. Treatments

4.4.1. Treatments Administered

4.4.1.1. Vaccine

The HydroVax-002 YFV vaccine is a yellow fever virus, Vero cell tissue culture-derived vaccine inactivated with hydrogen peroxide, formulated with 0.1% aluminum hydroxide.

4.4.1.2. Placebo and Diluent

Sodium Chloride Injection USP, 0.9% (NaCl 0.9%, Normal Saline) will be used as the placebo and diluent.

4.4.2. Method of Assigning Subjects to Treatment Groups (Randomization)

Once consented and upon entry of demographic data and confirmation of eligibility for the trial, the subject will be assigned to a treatment arm within each dose group (low dose and high dose) subjects will be randomly assigned to receive the study test product or placebo. Subjects will be block randomized so that 1 of the first 4 sentinel subjects will receive placebo and the other 3 active vaccine. In the expanded groups, 7 of the 8 or 9 subjects will be randomized to vaccine and 1 or 2 to placebo. Subjects will receive the same treatment for both vaccinations

Enrollment of subjects will be done online using the enrollment module of Advantage eClinical®. The randomization code will be prepared by statisticians at the SDCC and included in the enrollment module for the trial. Advantage eClinical® will generate a treatment assignment for each subject after the demographic and eligibility data have been entered into the system. A designated individual at each site will be provided with a code list for emergency unblinding purposes, which will be kept in a secure place.

4.4.3. Blinding

This is a partially-blinded clinical trial.

Study staff and investigators will not be blinded to dose group but, within dose groups, subjects, investigators, and study staff other than unblinded site research pharmacist (or other designated unblinded personnel

administering study product) will be blinded as to the subject's treatment assignment (vaccine vs. placebo). Laboratory personnel performing antibody assays will be blinded to dose group and treatment assignment.

The randomization scheme will be generated by the SDCC and provided to unblinded study personnel (i.e., research pharmacists performing study vaccination preparations and unblinded study vaccine administrators) at the clinical site.

An unblinded site research pharmacist will prepare the study product and an unblinded research nurse will inject the study product per the randomization assignment. The pharmacist will conceal the contents of the syringe by wrapping the syringe barrel with an overlay, opaque tape, or other equivalent material. In addition, the subject will be asked to look away when the vaccine is being administered.

The unblinded site research pharmacist and unblinded research nurse will not be involved in study-related assessments or have subject contact for data collection following study vaccine administration.

4.5. Immunogenicity and Safety Variables

The secondary immunogenicity outcome measure, seroconversion, is defined in [Section 3.3](#) above.

5. SAMPLE SIZE CONSIDERATIONS

A total of 25 subjects, age ≥ 18 and < 50 years of age, will be enrolled, where 10 subjects will receive 1 mcg of HydroVax-002 YFV, 10 will receive 5 mcg of HydroVax-002 YFV, and 5 will receive placebo. The study will consist of two dosing groups of HydroVax-002 YFV vaccine to be dosed sequentially. The initial dose of HydroVax-002 YFV to be evaluated in Group 1 will be 1 mcg and the next dose to be evaluated in Group 2 will be 5 mcg. The first 4 subjects of each group (3 receiving HydroVax-002 YFV and 1 receiving placebo) will serve as a sentinel subgroup.

The sample size of 10 vaccinated subjects in each dosage group with 5 subjects that receive placebo is small given the early stage (Phase 1) of the product's development, thus the precision of estimate for AEs is limited. Rare adverse events are not demonstrable in a clinical study of this size, however the probabilities of observing one or more AEs given various true event rates and sample sizes are presented in complete clinical protocol. If there are adverse events associated with HydroVax-002 YFV in this population, this study will have approximately 80% power to observe at least one such event in a dosage group size of 10 if the true rate is 15%. Comparisons will primarily be made between each vaccine dose group and placebo.

If there are no observed adverse events among the 10 vaccinated subjects in a dosage group associated with the investigational product, the upper 95% exact confidence bound for the incidence of adverse events will be 30.8%.

This study is not powered to detect small to moderate individual or pair-wise differences in immunogenicity outcomes between treatments.

6. GENERAL STATISTICAL CONSIDERATIONS

6.1. General Principles

All continuous variables will be summarized using the following descriptive statistics: n (non-missing sample size), mean, standard deviation, median, maximum and minimum. The frequency and percentages (based on the non-missing sample size) of observed levels will be reported for all categorical measures. In general, all data will be listed, sorted by treatment and subject, and when appropriate by visit number within subject. All summary tables will be structured with a column for each treatment (HydroVax-002 YFV, Placebo) and will be annotated with the total population size relevant to that table/treatment, including any missing observations.

Multiple observations within specific visit period are accepted. In the case of multiple observations within a specific window, the assessment value that is closest to the scheduled visit window will be used in the analyses for the post-baseline records. For screening and baseline visits, the last assessment value will be used. All the recorded data will be listed. If observations have the same distance to the scheduled assessment, the latest one will be used.

SAS version 9.4 or above will be used to generate all tables, figures, and listings.

6.2. Reporting Conventions

The mean, standard deviation, and other statistics will be reported to 1 decimal place greater than the original data. The minimum and maximum will use the same number of decimal places as the original data. Percentages will be reported to one decimal place. For all other estimators, the NEJM statistical reporting guidelines will be followed: results will be presented with no more precision than is of scientific value and is meaningful. For example, measures of association, such as odds ratios, will be reported to two or three significant digits. Results derived from models will be limited to the appropriate number of significant digits.

6.3. Timing of Analyses

Unblinded analyses of the primary and secondary safety, reactogenicity, and immunogenicity outcomes (Neutralization and viremia) and any supporting analyses of these outcomes will be performed once all subjects have completed the Day 57 post-dose 2 visit and the data are entered in the primary clinical database, validated and monitored according to the clinical monitoring plan. The results will be provided to the sponsor and PI for research planning purposes. Individual subject listings will not be generated at this point.

The remaining analyses, including generation of all individual subject listings, will be completed and the CSR generated after the last subject's last visit is completed, and the final clinical database, including all long-term safety follow-up data, is cleaned, monitored and locked.

6.4. Analysis Populations

A summary of all subjects excluded from the analyses will be provided.

6.4.1. Safety Population

The Safety Analysis population includes all eligible subjects who received at least one dose of study vaccine. In the case of mis-randomization subjects will be analyzed according to the study product actually received.

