9.3 Populations for Analyses

The Safety Analysis population includes all eligible subjects who received at least one dose of study vaccine.

The evaluable population includes all eligible subjects who received at least one dose of study vaccine and contributed both pre- and at least one post-study vaccination blood samples for testing for which valid results were reported.

The per protocol (PP) population excludes subjects who did not receive both doses of study vaccine or who had major protocol deviations, such as receipt of non-study vaccines during the time frame prohibited by the protocol or receipt of the second study vaccination substantially out of window.

In the case of mis-randomization subjects will be analyzed according to the study product actually received for all analysis populations.

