3.2. Endpoints

Primary Outcome Measures:

- Occurrence of all serious adverse events (SAEs) at any time during the study
- Occurrence of all Grade 3 unsolicited adverse events (AEs) from first vaccination through Day 29 after the second vaccination
- Occurrence of all Grade 3 laboratory toxicities from first vaccination through Day 15 after the second vaccination
- Occurrence of solicited local AE and reactogenicity signs and symptoms in the 7 days after each vaccination
- Occurrence of solicited systemic AE and reactogenicity signs and symptoms in the 7 days after each vaccination
- Occurrence of any AE through Day 29 after the second vaccination

Secondary Outcome Measures:

- Percentage of subjects achieving seroconversion ($\geq 1:10$ in plaque reduction neutralizing titer [PRNT₅₀] titer, at Day 29 after first vaccination and at Day 29 after second vaccination
- Geometric mean neutralizing titers at days 15 and 29 after first vaccination and at Days 15, 29, and 57 following second vaccination
- Reverse cumulative distribution curve of neutralizing titers on Days 15 and 29 after first vaccination and at Days 15, 29 and 57 after the second vaccination for each dose group and for all dose groups combined

Exploratory Outcome Measures:

- Geometric mean neutralizing titers at Day 180 following second vaccination
- Reverse cumulative distribution curve of neutralizing titers on Day 180 after the second vaccination for each dose group and for all dose groups combined

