6.4.2. Full Analysis Population

The full analysis (FA) population will consist of all subjects who received any study product (including control) and for whom immunogenicity endpoint data are available. In the case of mis-randomization subjects will be analyzed according to the study product actually received. Separate populations for each assay and/or dose may be needed if the availability of a sample's data varies across assay or if a subject is only eligible for analyses for one of the doses. For sake of simplicity, immunogenicity tables and figures will use a single "Full Analysis Population" label, however special cases and/or considerations for exclusions from assay- or dose-specific summaries will be provided in footnotes.

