APPENDIX 1. TABLE MOCK-UPS

Table 1: Ineligibility Summary of Screen Failures

Category	Reason/Criterion	N	%
Screened		x	-
Screened but not enrolled		x	100
Eligible but not enrolled	Any Reason	x	xx
	[reason 1]	x	xx
	[reason 2]	x	xx

Failing eligibility criteria	Any eligibility criterion ^a	x	xx
	Any inclusion criterion	x	xx
	[inclusion criterion 1]	x	xx
	[inclusion criterion 2]	x	xx

	Any exclusion criterion	x	xx
	[exclusion criterion 1]	x	xx
	[exclusion criterion 2]	x	xx

Denominator for percentages is the total number of subjects who were screened but not enrolled.

a: A subject could fail to meet more than one eligibility criterion. Thus, the sum of the counts of the individual reasons may add up to more than the total number of subjects who failed any eligibility criterion.

Table 2: Analysis Populations by Treatment Group

		HydroVax-002 YFV 1 meg (N=XX)		HydroVax-002 YFV 5 meg (N=XX)		Placebo (N=XX)		All Subjects (N=XX)	
Analysis Population	Reason Subjects Excluded	n	%	n	%	n	%	n	%
Safety Population	Included	x	x.x	x	x.x	x	x.x	x	x.x
	Excluded (Did not receive any vaccinations)	x	x.x	x	x.x	x	x.x	x	x.x
Post-Dose 1									
Full Analysis Population	Included	x	x.x	x	x.x	x	x.x	x	x.x
	Excluded	x	x.x	x	x.x	x	x.x	x	x.x
	Did not have pre- and post-baseline blood draws for YFV assay	x	x.x	x	x.x	x	x.x	x	x.x
	Did not receive any vaccinations	x	x.x	x	x.x	x	x.x	x	x.x
Per-Protocol Population	Included	x	x.x	x	x.x	x	x.x	x	x.x
	Excluded	x	x.x	x	x.x	x	x.x	x	x.x
	Did not receive any vaccinations	x	x.x	x	x.x	x	x.x	x	x.x
	Did not receive both vaccinations	x	x.x	x	x.x	x	x.x	x	x.x
	[Insert other reasons, e.g. protocol deviation]	x	x.x	x	x.x	x	x.x	x	x.x
Post-Dose 2									
Full Analysis Population	Included	x	x.x	x	x.x	x	x.x	x	x.x
	Excluded	x	x.x	x	x.x	x	x.x	x	x.x
	Did not have pre- and post-baseline blood draws for YFV assay	x	x.x	x	x.x	x	x.x	x	x.x
	Did not receive any vaccinations	x	x.x	x	x.x	x	x.x	x	x.x
Per-Protocol Population	Included	x	x.x	x	x.x	x	x.x	x	x.x
	Excluded	x	x.x	x	x.x	x	x.x	x	x.x
	Did not receive any vaccinations	x	x.x	x	x.x	x	x.x	x	x.x
	Did not receive both vaccinations	x	x.x	x	x.x	x	x.x	x	x.x
	[Insert other reasons, e.g. protocol deviation]	x	x.x	x	x.x	x	x.x	x	x.x

N = All enrolled subjects

Implementation Note: Above displays how dose-specific summaries will be presented if subject eligibilities differ by dose. Similar breakdowns by assay will be included if needed.

Table 3: Subject Disposition by Treatment Group

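### The Safety population text admits only eligible dosed subjects, against SAP Table 2; the primary any-AE endpoint has no table row; and laboratory toxicity loses the protocol's moderate-or-severe dichotomy and exact interval

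*SAP*

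**What the plan says.** **Population.** SAP 6.4.1 states: "The Safety Analysis population includes all eligible subjects who received at least one dose of study vaccine". Protocol 9.3 uses the same sentence, and its evaluable population carries the same condition: "The evaluable population includes all eligible subjects who received at least one dose of study vaccine". The SAP's Full Analysis population does not; it takes "all subjects who received any study product (including control) and for whom immunogenicity endpoint data are available". In SAP Table 2, the only reason for leaving the Safety population is "Excluded (Did not receive any vaccinations". SAP 6.4 adds: "A summary of all subjects excluded from the analyses will be provided". For the analysis after the Day 57 post-dose 2 visit, SAP 6.3 says: "Individual subject listings will not be generated at this point".

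**Any-AE endpoint.** SAP 3.2 lists six primary outcome measures. One is "Occurrence of any AE through Day 29 after the second vaccination". Table 9, the overall AE summary, has separate rows for local solicited, systemic solicited, unsolicited, laboratory and serious events, and for AEs leading to early termination. Its footnote allows a subject to be counted in more than one main category.

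**Laboratory and solicited method.** Protocol 9.4.2 takes solicited AEs and laboratory toxicities at each subject's worst severity, reduces them to none or mild versus moderate or severe, and summarises the rates with exact confidence intervals. SAP 8.4 plans a distribution by severity. Tables 28 and 29 show n and % by grade with no interval column, and Table 9 has no interval column at all. Table 10 has intervals by severity level but no combined moderate-or-severe row. Tables 23 and 24 have interval columns whose method is a placeholder.

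**The concern.** Safety is the primary objective of this first-in-human trial, and each group is small: 10, 10 and 5. Three things are at stake.

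- An exposed subject could leave the denominators, and the numerators, of the primary safety tables because of an eligibility finding unrelated to exposure. At the Day 57 analysis there are no subject listings, so the tables carry the result.
- A primary endpoint is defined in SAP 3.2 but no table is set up to report it.
- The protocol's stated summary for laboratory toxicity is not carried into the shells, and SAP section 10, which records changes in planned analyses, does not mention this.

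**Working it through.** **1. The plan's own figure.** SAP section 5 and protocol 9.2.1 give an upper exact 95% bound of 30.8% for no events in 10. The two-sided Clopper-Pearson upper limit for 0/n is 1 − 0.025^(1/n). For n = 10 it is 30.8%, which reproduces. The one-sided version, 1 − 0.05^(1/10), is 25.9%, so the plan uses the two-sided limit.

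**2. Effect of dropping one dosed but ineligible subject.** The number of such subjects is unknown; one per group is an assumption.

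| Group | All dosed | One dropped |
|---|---|---|
| Dose group, 0 events | 0/10: upper bound 30.8% | 0/9: 33.6% |
| Placebo, 0 events | 0/5: 52.2% | 0/4: 60.2% |
| Dose group, the dropped subject had the only event | 1/10: 0.3% to 44.5% | 0/9: 0% to 33.6% |

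The last row is the one that matters most: the event leaves the table along with the subject.

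**3. Is any AE reported somewhere else?**

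- Table 9: separate categories, no combined row.
- Table 10, any-symptom rows: solicited events only.
- Tables 23 and 24, any-SOC rows: unsolicited events only.
- Tables 25 to 27: unsolicited only, with a last window that runs to Day 57.
- Tables 28 and 29: laboratory results only.
- Figures 6 to 9: titled as AE incidence and introduced in SAP 8.1.2 under unsolicited events. Their content is not shown, so it cannot be checked.

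The count cannot be recovered from the categories. Suppose, purely as an illustration, that 4/10 subjects have a solicited event, 3/10 an unsolicited event and 2/10 a laboratory toxicity, with no other events.

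- Without laboratory events: minimum max(4, 3) = 4, maximum 4 + 3 = 7. That is between 4/10 (exact 95% CI 12.2% to 73.8%) and 7/10 (34.8% to 93.3%).
- With laboratory events: minimum 4, maximum 4 + 3 + 2 = 9. The upper end becomes 9/10 (55.5% to 99.7%).

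**4. Do laboratory abnormalities count as AEs?** The SAP does not say for this endpoint. The protocol points to yes. Section 8.5.1 includes abnormal laboratory findings in the AE definition. Section 7.1.1 speaks of grading clinical safety laboratory AEs. Section 8.2.2 requires relatedness and action taken for every result that meets the grading criteria. The note to Appendix A says that a value within the normal limits is not a Grade 1 AE, which implies that other graded values are.

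**5. Protocol 9.4.2 against the shells.**

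| Item in protocol 9.4.2 | Laboratory (Tables 9, 28, 29) | Solicited (Table 10) |
|---|---|---|
| Worst severity per subject | Yes: maximum-severity rows in Tables 28 and 29 | Yes, for the any-symptom counts |
| None or mild versus moderate or severe | No | No |
| Exact interval | No | Interval column, method not named |

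Illustration: worst grade 2 in 2/10 and worst grade 3 in 1/10 give a moderate-or-severe rate of 2 + 1 = 3/10, exact 95% CI 6.7% to 65.2%, and a Grade 3 rate of 1/10, CI 0.3% to 44.5%. The shells have a place for neither interval.

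**6. Does the choice of exact method matter?** SAP section 8 names no method. The only one named in the SAP is Blaker's, in section 9 for immunogenicity. For 0/10, Blaker's interval is 0% to 28.3%, against 0% to 30.8% by Clopper-Pearson; for 3/10 it is 8.7% to 61.9%, against 6.7% to 65.2%. Only Clopper-Pearson agrees with the bound in SAP section 5.

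**The case against.** The case against is that these are clean-ups in a descriptive Phase 1 plan. Much of it is fair, and it rules out several stronger readings that a reader might infer.

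- *An ineligible subject would disappear.* Not so. Exclusions are summarised (SAP 6.4), Table 4 counts eligibility deviations, and the final listings remain. Protocol section 5 allows no exemptions and eligibility is rechecked on both vaccination days, so the case may never arise. Table 2 suggests that all dosed subjects are meant. What stands is that the text and the shell give different answers, and the text is the rule.
- *Placebo recipients are left out because the text says study vaccine.* Not supported: Table 2 has a placebo column for this population.
- *The Grade 3 laboratory endpoint is not reported.* Wrong. Table 9 already has a Grade 3 laboratory row regardless of relatedness, with n and %. Only its interval is missing.
- *The interval method is wholly open.* No. Protocol 9.4.2 requires exact intervals for solicited, laboratory and unsolicited events; only the particular exact method is open.
- *There is no rule on laboratory events.* Too strong, given the protocol text in step 4. The SAP merely fails to carry it into the any-AE endpoint.
- *Late events will contaminate the Grade 3 endpoint.* The endpoint is "Occurrence of all Grade 3 unsolicited adverse events (AEs) from first vaccination through Day 29 after the second vaccination", and Tables 9, 23 and 24 state no onset cut. But routine non-serious collection ends at that same visit (protocol 8.5.4). Only late medically attended, serious or new chronic events could enter, so the effect is negligible and no change is asked for.

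It is also true that a moderate-or-severe count per laboratory parameter can be had by adding two columns of Table 28, and an interval computed from n and N. The any-AE count cannot be recovered in this way, and the endpoint remains binding under SAP 3.2 whatever the shells show.

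**Conclusion.** The point holds in three parts, as something that should be corrected before the SAP is applied. No figure in either document is wrong, and no data are lost.

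1. The eligibility condition contradicts Table 2. Its effect depends on an ineligible subject being dosed. Assuming one with no events observed, the upper bound rises by 33.6 − 30.8 = 2.8 percentage points in a dose group and by 60.2 − 52.2 = 8.0 in placebo. If that subject had the only event, 1/10 becomes 0/9.
2. One of six primary endpoints has no table row and cannot be derived from those planned. This rests on the table shells; Figures 6 to 9 cannot be seen and might cover part of it.
3. The SAP departs from protocol 9.4.2 without declaring it: no dichotomy and no interval for laboratory toxicity, and no moderate-or-severe row for solicited events.

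The counts used to illustrate parts 2 and 3 are invented. They show what could not be read from the tables, not an expected result.

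**What to change.** - **SAP 6.4.1:** define the Safety population as all subjects who received at least one dose of study product (vaccine or placebo), analysed as treated. Record the change in SAP section 10 and align protocol 9.3 at its next amendment.
- **Table 9:** add a row for subjects with at least one AE of any type through Day 29 after dose 2, with an exact 95% CI. Count each subject once across solicited, unsolicited and serious AEs and graded laboratory abnormalities. If wanted, show the row without laboratory events as well.
- **Table 9, existing Grade 3 laboratory row:** add an exact 95% CI.
- **Table 28, maximum-severity rows:** add the moderate-or-severe proportion with an exact 95% CI.
- **Table 10:** add a moderate-or-severe row.
- **SAP section 8 and the footnotes of Tables 23 and 24:** name the exact method. Clopper-Pearson matches the stated 30.8%.

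The cost is SAP wording and shell edits, with no new data. Changing protocol 9.3 needs IRB approval (protocol 10.1.1.4), so it need not be a separate amendment.
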